6.3. Protocol Deviations

All important protocol deviations will be summarized for the SAF by study cohort and overall as described below:

- The number of unique participants with at least one important protocol deviation as well as the number of participants in each important protocol deviation category will be presented by default descriptive summary statistics for categorical variables.

Important protocol deviations which lead to exclusion from the PPS will be summarized for the SAF by study cohort and overall as described below:

- The number of unique participants with at least one important protocol deviation leading to exclusion from the per protocol set as well as the number of participants in each important protocol deviation category will be presented by default descriptive summary statistics for categorical variables.

A listing of all participants with one or more important / non important protocol deviations will be presented for the Safety Analysis Set. Protocol deviations which resulted in removal from the PPS will be indicated.

6.4. Demographic and Other Baseline Characteristics

6.4.1. Demographic Characteristics

Demographic characteristics will be summarized for the Safety Analysis Set by treatment group and overall as described below. All missing data will be presented as part of a missing category. Standard descriptive statistics will be presented for the continuous variables of:

- Age (years) at time of informed consent
- Height (cm) at screening visit
- Weight (kg) at screening visit

- Body mass index (kg/m^2) at screening visit, calculated as (body weight / height²) where weight is in kg and height is in m and presented to one decimal precision.

Total counts and percentages of participants will be presented for the categorical variables of:

- Age group (years):
 - < 65
 - ≥ 65 to < 75
 - ≥ 75
- Race
- Ethnicity

Demographic characteristics will be listed for the Safety Analysis Set.

6.4.2. Baseline Characteristics

Baseline characteristics will be summarized for the Safety Analysis Set by treatment group and overall as described below. All missing data will be presented as part of a missing category. Missing categories will only be displayed if missing data are present.

Standard descriptive statistics will be presented for the continuous variables of:

- Time from date of initial diagnosis of prostate adenocarcinoma to informed consent (months) [Calculated as (date of informed consent – date of initial diagnosis of prostate adenocarcinoma + 1)/30.4375]
- If historic tumour sample has been collected: Time from historic tumour sample collection date to informed consent (months) [Calculated as (date of informed consent – date of historic tumour sample collection + 1)/30.4375]
- If radical prostatectomy has been performed: Time from date of radical prostatectomy to informed consent (months) [Calculated as (date of informed consent – date of radical prostatectomy + 1)/30.4375]
- If non-metastatic (M0) disease has been verified: Time from non-metastatic disease confirmed to informed consent (months) [Calculated as (date of informed consent – date of non-metastatic disease confirmed [Date Nonmetastatic (M0) Disease Confirmed on Prostate Adenocarcinoma History eCRF page]+ 1)/30.4375]
- eCRF PSA Doubling Time (months)
- Independently calculated PSA doubling time (months): PSA doubling time will be independently calculated based on historic PSA values collected on the Prostate Adenocarcinoma History eCRF page. The 3 most recent PSA values will be used to calculate doubling time where the date of assessment \geq (date of informed consent – 2*365.25). The first included date of assessment, *date1*, will be treated as Time 0

and other assessments will have time, t , calculated as $datej-date1+1$. The linear regression model will be fitted as:

$$\ln(\text{PSA}(t)) = \ln(\text{PSA}(0)) + \beta t.$$

The PSA doubling time (months) will be calculated as: $\ln 2 / (\beta \times 30.4375)$.

Total counts and percentages of participants will be presented for the categorical variables of:

- Confirmation of adenocarcinoma (Histologically, Cytologically)
- Radical prostatectomy (Yes, No)
- Nonmetastatic (M0) disease verified (Yes, No)
- Previous treatment with radiation (Yes, No)
 - Type of radiotherapy (Definitive external beam radiation, Salvage external radiation therapy)
- Previous treatment with brachytherapy (Yes, No)
 - Low Dose, High Dose
- Radical Prostatectomy (Yes) (External Beam Radiotherapy, No External Beam Radiotherapy) [From the prostate adenocarcinoma history eCRF page where “Was the participant treated by radiation? Is Yes/No”]
- Radical Prostatectomy (No) (Brachytherapy Only, External Beam Radiotherapy Only, Brachytherapy and External Beam Radiotherapy)
- Any other prior malignancy within the last 5 years (Yes, No)
- T Stage (T1, T2, T3, T4)
- Gleason Score $\leq 6, 7, 8, 9, 10$
- Gleason pattern ($\leq 6, 3+4, 4+3, 8, \geq 9$)
- Baseline PSA (ng/ml) ($<0.5, 0.5-1, 1-2, 2-5, 5-10, 10-20, >20$) [Using the serum PSA assessment from the screening period]
- PSA doubling time as recorded in the ‘Prostate Adenocarcinoma History’ eCRF page (0- <6 months, 6-12 months, >12 months)

No formal tests of statistical significance will be performed on the demographic and baseline characteristics data.

The Gleason pattern categories will combine categories captured in the ‘Prostate Adenocarcinoma History’ eCRF page gleason pattern question as:

- ≤ 6 (Captured as ‘Less than or Equal to 3+3’)
- $3+4$
- $4+3$
- 8 (Captured as ‘4+4’, ‘3+5’, ‘5+3’)
- ≥ 9 (Captured as ‘4+5’, ‘5+4’, ‘5+5’)

Baseline characteristics will be listed for the Safety Analysis Set.

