6.1. General Principles

All data processing, summarization and analyses will be performed using Fortrea's SAS Environment / Version 9.4 (or later) of the SAS® statistical software package.

The default summary statistics for quantitative variables will be the number of observations (n), mean, standard deviation (SD), median, 25th percentile, 75th percentile, minimum (min) and maximum (max), for those participants with data. The 25th and 75th percentiles will only be presented when the denominator is at least 10 participants.

For qualitative variables, the number (n) and percentage (%) of participants with non-missing data per category will be the default summary presentation, and where appropriate and present, the number of missing values as a “Missing” category. The number of participants in the analysis population will be used as the denominator for percentages calculation, unless stated otherwise in TFLs mock shell(s).

All statistical comparisons will be made using two-sided tests at the $\alpha=0.05$ significance level unless specifically stated otherwise. All null hypotheses will be of no treatment difference. All alternative hypotheses will be two-sided.

All laboratory test results will be received from central laboratories, and the results will be provided in both standard internal and conventional units. For the TFLs, the results will be summarized or presented in International System of Units (SI) units. Refer to Appendix of the TFLs mock shells for the SI unit corresponding to each laboratory test.

Refer to Appendix of the TFL shells for the precision level in which each laboratory test is reported by the central laboratories.

Specifications for table, figures and data listing formats can be found in the TFL shells specifications for this study. Please refer to “2. General Format Guidelines” section within TFL shells for more details on presentation of results.

In summary tables, participants will be presented by the following treatment groups::

- IM/IM Low Dose
- IM/IM Full Dose
- IM/IV Full Dose

If a participant does not receive a second dose of investigational product they will be assigned to the treatment group IM/IM Full.

In listings, participants will be presented by the following treatment groups:

- Cohort 1: IM/IM Low Dose
- Cohort 2: IM/IM Full Dose
- Cohort 3: IM/IV Full Dose

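### The SAP's independently calculated PSA doubling time stretches the first interval by a day and has no rule for a zero or negative slope, so its baseline mean and SD can be meaningless

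*SAP*

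**What the plan says.** SAP 6.4.2 lists two doubling times as continuous baseline variables: the one entered on the eCRF, and one recalculated from the historic PSA values on the Prostate Adenocarcinoma History page. For the recalculated one:

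- **Data.** "The 3 most recent PSA values will be used to calculate doubling time where the date of assessment" falls no more than two years (2 × 365.25 days) before consent.
- **Time scale.** The first included date "will be treated as Time 0". The "other assessments will have time" t equal to their date minus the first date, plus one.
- **Model.** The regression is ln PSA(t) = ln PSA(0) + βt.
- **Conversion.** "The PSA doubling time (months) will be calculated as" ln2/(β × 30.4375). No condition is placed on β.
- **Summary.** "Standard descriptive statistics will be presented for the continuous variables of" this list, by treatment group and overall. SAP 6.1 defines the default: "The default summary statistics for quantitative variables will be the number of observations (n), mean, standard deviation (SD), median", with minimum and maximum, and quartiles when the denominator is at least 10.

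The categorical table in the same section (0 to <6, 6 to 12, >12 months) applies to the eCRF value only. Protocol inclusion criterion 8 requires a doubling time of 12 months or less and gives no calculation method.

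**The concern.** There are two separate faults in one derivation.

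The first is the time origin. Adding one to every date, or to none, leaves the slope unchanged. Adding it to all but the first lengthens the first interval by a day, which makes a rising slope too shallow and the doubling time too long.

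The second is the behaviour of the formula near zero slope. Doubling time tends to plus infinity as β falls to zero, is undefined at zero, and comes back from minus infinity once β is negative. Men with almost the same, nearly flat PSA can therefore get values of opposite sign and very large size. A mean or SD over such values describes nothing. Phase 1 cohorts are planned at 3–6, 6 and 6 men, so one man can dominate a column. The row is meant to tell the reader how fast the disease was moving at entry, and its mean could come out negative or absurdly long. At β = 0 the programmer would have to improvise.

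**Working it through.** The documents give no numerical doubling time, so there is no figure to reproduce. The rule was applied literally. PSA values, sample spacings and the other men's doubling times are illustrative assumptions. Formulas, cohort sizes and summary statistics come from SAP 6.4.2, 6.1 and Table 2 (Phase 1 Trial Cohorts).

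**1. The extra day.** For three samples d days apart, true times are 0, d, 2d and SAP times are 0, d+1, 2d+1. For exactly exponential growth, least squares on SAP times gives

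fitted slope / true slope = (2d² + d) / (2d² + 2d + 2/3),

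and doubling time is inflated by the reciprocal.

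| Spacing d (days) | Inflation factor | Inflation | A true 6 months becomes |
|---|---|---|---|
| 180 | 65,160.67 / 64,980 | 0.28% | 6.02 |
| 90 | 16,380.67 / 16,290 | 0.56% | 6.03 |
| 30 | 1,860.67 / 1,830 | 1.68% | 6.10 |

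With plain elapsed days the fit returns 6.00 each time.

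**2. A slightly falling PSA.** Take 0.50, 0.55 and 0.48 ng/mL at days 0, 90 and 180, so SAP times are 0, 91 and 181.

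- ln PSA: -0.6931, -0.5978, -0.7340; mean -0.6750.
- Time deviations from the mean of 90.667: -90.667, 0.333, 90.333.
- Sum of cross-products -3.656; sum of squares 16,380.67; β = -0.0002232 per day.
- Doubling time = 0.6931 / (-0.0002232 × 30.4375) = -102.0 months.

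With plain elapsed days it is -100.4, so the extra day is not what makes it negative.

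**3. Effect on the mean.** Suppose the other men average 6.67 months.

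- Six-man cohort: (5 × 6.67 - 102.0) / 6 = -11.4 months.
- All of Phase 1 at about 25 men: (24 × 6.67 - 102.0) / 25 = +2.3 months.

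The mean is negative when the negative value exceeds (n - 1) times the others' mean in size. Here that holds up to n = 16 (15 × 6.67 = 100.05) and not from n = 17 (16 × 6.67 = 106.72).

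**4. A slightly rising PSA.** 1.00, 1.01 and 1.02 at the same days gives +208 months. With five others at 4, 5, 6, 7 and 8 months, the mean is (30 + 208.1) / 6 = 39.7.

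**5. An exactly flat PSA.** β = 0 and the formula divides by zero.

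**6. The median.** Those five men alone have a median of 6. Adding the -102-month man gives 5.5 and adding the +208-month man gives 6.5, while the means are -12.0 and 39.7.

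**7. Could an enrolled man produce this?** PSA 0.20, 0.35, 0.50, 0.72, 0.71 and 0.70 every 90 days gives 8.2 months when all six values are fitted on elapsed days. The SAP's rule on the last three gives -146 months. Because the protocol fixes no method, both results can belong to the same man.

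**The case against.** The strongest reply is that little depends on this row. The SAP already plans the median, minimum and maximum, and lists baseline characteristics by participant, so an odd value would be visible. The eCRF doubling time is summarised separately, both continuously and by category. Falling values should be uncommon in men enrolled with a doubling time of 12 months or less, and the documents give no frequency. The SAP never says in words that negative values are averaged, and the table shells, which are not public, might deal with them. An undefined value could go into the missing category that SAP 6.4.2 provides. All of this stands and limits the weight of the point. It does not repair the rule: the extra day is explicit, and nothing in the SAP text keeps a negative value out of the default mean and SD.

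Several stronger readings are tempting but not supported:

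- **That a flat PSA makes the mean negative.** An exactly flat PSA is undefined. Only a slightly falling one is negative, and a slightly rising one pulls the mean up.
- **That the extra day affects eligibility.** With monthly samples 11.9 months would become 12.1, but nothing in the SAP compares this value with 12, and criterion 8 is not tied to this formula.
- **That a man with no PSA growth makes the group look fast-doubling.** A negative mean reads as invalid, not as fast.
- **That the overall Phase 1 mean must turn negative.** In the example above it stays at +2.3 months.

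**Conclusion.** The derivation is wrong as written in two independent ways, and the consequence is minor. The one-day error inflates doubling time by about 0.3% to 1.7% for samples 180 to 30 days apart, and by more if they are closer; the documents do not state the spacing of historic PSAs. The missing rule for β ≤ 0 matters more. A single nearly flat, slightly falling PSA can make a six-man cohort mean about -11 months, given the assumed series and an average of 6.67 months in the other five. A nearly flat, rising PSA distorts the mean and SD in the other direction. How often either would occur cannot be judged from the documents.

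The damage is confined to the mean and SD in one descriptive baseline row. A reader might infer that the PSA response results or the selection of participants are affected. They are not: no eligibility decision, efficacy analysis or safety analysis in the documents uses this value.

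**What to change.** In SAP 6.4.2:

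1. Define t as the assessment date minus the first included date for all samples, so that the first is 0 and no day is added to the others.
2. State that men with β ≤ 0 are reported as a count in a 'not doubling' category and left out of the mean and SD.
3. Make the median the main summary. A very long positive value still enters the mean under rule 2, so the mean should not lead.
4. Tabulate the independent value in the categories already used for the eCRF value (0 to <6, 6 to 12, >12 months), plus 'not doubling'.

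The cost is one corrected formula, one sentence and a few table rows. Data collection, sample size and trial conduct do not change.

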6.4.3. Medical History

Medical history is defined as any condition that the participant may have had prior to start of first dose of VTP-850 in the study, including any chronic conditions diagnosed prior to entry in the study.

Medical history will be coded using the Medical Dictionary for Regulatory Activities (MedDRA) [version 25.1 or later version]. Medical history records will be summarized for the Safety Analysis Set by treatment group and overall as follows:

- The number and percentage of participants with at least one medical history record will be presented.
- The number and percentage of participants with at least one medical history record within each primary SOC and PT will be presented. The summary will be sorted using the internationally agreed order for SOC and using descending order of overall numerical counts for PT. Where terms tie, these will be sorted alphabetically.

Medical history records will be listed by-participant and within-participant by medical history start date for the Safety Analysis Set.

6.4.4. Prior and Concomitant Medications

All medications will be coded using the WHO Drug Global Dictionary, Format B3 [Version September 2022 (or a later version if updated during the study)], Anatomical Therapeutic Chemical (ATC) Classification codes. As per protocol Section 6.10, this will include all vaccines that the participants received any time from 6 months prior to enrolment and any time during the trial. Any prior adenoviral-vectored vaccine administered at any time should be recorded (e.g. COVID-19 vaccines made by Janssen/Johnson & Johnson or by AstraZeneca).

Prior medications and concomitant medications are defined as follows:

- Prior medications are those taken up to 30 days prior to day 1 with a stop date prior to the start of the Intervention Period.
- Concomitant medications are those with a start date on or after the start of the Intervention Period, or those with a start date before the start of the Intervention Period and either a stop date on or after the start of the Intervention Period, or are ongoing at the end of the study.

Prior procedures and concomitant procedures are defined as follows:

- Prior procedures are those taken up to 30 days prior to day 1 with a stop date prior to the start of the Intervention Period.
- Concomitant procedures are those with a start date on or after the start of the Intervention Period, or those with a start date before the start of the Intervention Period and either a stop date on or after the start of the Intervention Period, or are ongoing at the end of the study.

See Section 5.2.3 for imputation of missing or partial dates for medication.

Prior and concomitant medications will be summarized separately for the Safety Analysis Set by treatment group and overall as follows:

- The number and percentage of participants with at least one prior / concomitant medication will be presented.
- The number and percentage of participants with at least one prior / concomitant medication within each Anatomical Group (ATC Level 1), Therapeutic Subgroup (ATC Level 2), and preferred term will be presented. The summary will be sorted using numerical counts by descending order of Anatomical Group, then descending order of Therapeutic Subgroup, then descending order of preferred term in the total column. Where groups or terms tie these will be sorted alphabetically.

Prior medications, prior procedures and concomitant medications will be listed separately for the Safety Analysis Set. In the listings the relative start and stop day of prior / concomitant medication use will be calculated relative to the first dose date and time of VTP-850. If the concomitant medication is “Ongoing” it will be indicated as such in the listing and the relative stop day will not be calculated. Adenoviral-vectorized vaccines will be marked in the listings and identified via clinical review of the prior and concomitant medications prior to database lock. Prior and concomitant procedures will be listed only.

6.5. Measurements of VTP-850 Compliance

VTP-850 is administered at the site, under the supervision of qualified personnel, and so treatment compliance measurement is not applicable.

6.6. Efficacy

No adjustment for multiplicity will be made. Without adjustment for multiplicity, results should be interpreted with caution as the probability of a type I error increases.

6.6.1. Primary Efficacy Analysis

Primary Efficacy Analysis is not applicable.

6.6.2. Secondary Efficacy Analysis

6.6.2.1. PSA Response to VTP-850

The number, proportion and 90% confidence intervals (CI) of participants with a confirmed PSA response, defined as a $\geq 50\%$ reduction in serum PSA compared to baseline and measured twice consecutively, at least 2 weeks apart, will be summarized by timepoint (using visit windows defined in Section 5.1) and overall for each treatment group using the EES. The proportion at each time point will present the participants who have the 1st (if confirmed at least 2 weeks later) measurement where the $\geq 50\%$ reduction in serum PSA has been met compared to baseline. Percentage change in PSA will be calculated as $100 \times (\text{PSA value (ng/ml) at visit } i - \text{PSA value at baseline}) / (\text{PSA value at baseline})$. The 90% CIs will be calculated using Jeffrey's confidence limits. The maximum percentage change in PSA from baseline will be summarized continuously by treatment group. A waterfall plot of maximum percentage change in PSA from baseline will be produced by treatment group with bars of the waterfall plot produced using different colours to represent prior radical prostatectomy or definitive external beam radiation (Yes, No). Per cohort, a spaghetti plot will display each participant's percentage change in PSA (e.g. each patient's baseline measurement will display as 100%) by the number of days since the day 1 dosing visit. On each participant's line, a marker will indicate the study day each dose occurred.

Example of this calculation of confirmed PSA response are displayed in Table 7 and Table 8.

Table 7: Calculation of PSA Response Example

Participant	Timepoint	Study Day	PSA Value (ng/mL)	PSA change from baseline	PSA absolute change from nadir	PSA percent change from nadir
1	Baseline	1	1.5			
1	Day 29	29	1.6	6.67%		
1	Day 57	57	1.0	-33.33%		
1	Day 64	64	0.9	-40.00%		
1	Month 4	122	0.8	-46.67%		
1	Month 5	153	0.2	-86.67%		
1	Month 6	164	0.2	-86.67%		
1	Month 7	215	0.3	-80.00%	0.1	50.00%
1	Month 8	246	0.3	-80.00%	0.1	50.00%
1	Month 9	271	0.5	-66.67%	0.3	150.00%

- Responder = Yes
- First observed PSA response = Month 5

- PSA progression (Defined in Section **Error! Reference source not found.**) = Month 9 (since there's a $\geq 25\%$ increase from PSA nadir AND an absolute increase of ≥ 0.2 ng/mL)
- Durable PSA response at Month 8 (Defined in Section 6.6.2.2) = Yes (since a confirmed PSA response has occurred and the criteria for PSA progression has not been met)

Table 8: Calculation of PSA Response Example

Participant	Timepoint	Study Day	PSA Value (ng/mL)	PSA change from baseline	PSA absolute change from nadir	PSA percent change from nadir
1	Baseline	1	1.6			
1	Day 29	29	1.3	-18.75%		
1	Day 57	57	1.05	-34.38%		
1	Day 64	64	0.90	-43.75%		
1	Month 4	122	0.80	-50.00%		
1	Month 5	152	0.80	-50.00%		
1	Month 6	164	0.81	-49.38%	0.01	1.25%
1	Month 7	226	0.82	-48.75%	0.02	2.50%
1	Month 8	256	0.85	-46.88%	0.05	6.25%
1	Month 9	282	0.75	-53.13%	-0.05	-6.25%

- Responder = Yes
- First observed PSA response = Month 4
- PSA progression = No PSA progression
- Response at Month 8 = Yes (A confirmed PSA response has occurred and no PSA progression)

6.6.2.2. Durable PSA Response to VTP-850 at Month 8

If more than three participants have a confirmed PSA response at month 6 then the number, proportion and 90% CIs of participants with a durable PSA response (having a confirmed PSA response without PSA progression or on or before Month 8) will be presented for each treatment group using the EES. Participants with missing PSA data at Month 8 will have a durable PSA response imputed as described previously in Section 5.2.1. Otherwise, if participants are missing PSA data at Month 8 they will be treated as non-responders. The same summary will also be presented among participants who have a durable response at Month 6.

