3 OBJECTIVES AND ENDPOINTS

| Primary Objective | Primary Endpoints |
|--|---|
| To evaluate the safety of VTP-850 prime-boost regimens, with the booster dose administered either IM or IV, and establish an RP2R | 
 Number and proportion of participants with AEs, treatment-related AEs, \geGrade 3 AEs, \geGrade 3 treatment-related AEs, serious adverse events, and treatment-related serious adverse events Number and proportion of participants with clinically significant laboratory values Change from baseline for laboratory tests and vital sign measurements at each time point of collection |
| Secondary Objectives | Secondary Endpoints |
| To evaluate the PSA response rate to VTP-850 | 
 Percentage of participants with \ge50% reduction in serum PSA compared to baseline at any time, based on two consecutive measurements, at least 2 weeks apart |
| To evaluate the durable PSA response rate to VTP-850 | 
 Percentage of participants with confirmed PSA response compared to baseline without having PSA progression on or before Month 8. |
| To evaluate the duration of PSA response to VTP-850 (for the subset of participants with PSA response) | 
 Duration of PSA response (for the subset of participants with PSA response), defined as time from date of first dose of VTP-850 to the date of PSA progression (i.e., an increase of \ge25% and an absolute increase of 0.2 ng/mL or more from nadir) |
| To assess the Metastasis-free Survival (MFS) and Time to Metastases (TTM) of the subset of participants with PSA response | 
 MFS is defined as the time from date of first dose of VTP-850 until metastatic disease by conventional imaging (CT/MRI and/or technetium-99 bone scan) or death from any cause, whichever occurs first TTM is defined as the time from date of first dose of VTP-850 until metastatic disease by conventional imaging (CT/MRI and/or technetium-99 bone scan) 
Note that MFS and TTM events do not include local progression events, e.g., progression in pelvic lymph nodes below the aortic bifurcation.
 |
| To assess the time to start of ADT for the participants with PSA response | 
 Time from date of first dose of VTP-850 to the earliest of the start of ADT or the date when criteria to start ADT are met |
| Exploratory Objectives | Exploratory Endpoints |

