11.2.3 Secondary Endpoint Analyses

11.2.3.1 PSA Response to VTP-850

The number, proportion, and 90% confidence interval (CI) of participants with a PSA response, defined as $\geq 50\%$ reduction in serum PSA compared to baseline and measured twice consecutively, will be summarised by timepoint and overall. This will be further broken down by whether the participants had prior radical prostatectomy or prior external beam radiation. The maximum PSA reduction from baseline will be summarised, as well as by whether participants had prior radical prostatectomy, external beam radiation or brachytherapy.

11.2.3.2 Durable PSA Response to VTP-850 at Month 8

The number, proportion and 90% CI of participants with a durable PSA response at Month 8 will be summarised, among all participants and among those with a response by Month 6. Durable PSA response is defined as having follow-up through Month 8 and a confirmed PSA response without having PSA progression (i.e., an increase relative to nadir of $\geq 25\%$ and an absolute increase of 0.2 ng/mL or more) on or before Month 8. This will be further summarised by whether the participants had prior radical prostatectomy, external beam radiation or brachytherapy.

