This SAP will cover the analyses for the Phase 1 part of the study. Phase 2 has not commenced and therefore any analyses related to or more applicable to the phase 2 part of the study are not covered in this SAP. A separate SAP will be written to cover the phase 2 part of the study in future.

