2.2.2.1. Endpoints for the Secondary Objective(s)

The following are the relevant endpoints corresponding to the secondary objectives in the phase 1 part of this study:

- Percentage of participants with $\geq 50\%$ reduction in serum PSA compared to baseline at any time, based on two consecutive measurements at least 2 weeks apart
- Percentage of participants with confirmed PSA response compared to baseline without having PSA progression on or before Month 8

Full details for each endpoint are provided in Section 6.6.2.

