2.3. Sample Size and Power

A total of approximately 144 participants will be enrolled. Approximately 25 participants will be enrolled into the Phase 1 of the study. A sample size of approximately 125 participants will be eligible for inclusion in the Phase 2 efficacy evaluation. Full details of the sample size calculation are provided in the protocol Section 11.4.

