6.8.1. Pharmacokinetic Analysis

Not Applicable.

7. Changes in the Conduct of the Study or Planned Analysis

The change from baseline for electrocardiograms have been added as a primary endpoint for the primary objective of evaluating the safety of VTP-850 prime-boost regimens.

8. Appendices

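### The Phase 1 SAP shows durable PSA response only if more than three participants respond at Month 6: an undeclared, outcome-dependent narrowing of a secondary endpoint that the protocol reports without condition

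*SAP*

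**What the plan says.** Protocol Section 3 makes durable PSA response a secondary endpoint: "Percentage of participants with confirmed PSA response compared to baseline without having PSA progression on or before Month 8". Protocol 11.2.3.2 fixes its analysis: "The number, proportion and 90% CI of participants with a durable PSA response at Month 8 will be summarised, among all participants", and also among those who responded by Month 6. No minimum number of responders is attached in either place.

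The SAP is limited in scope: "This SAP will cover the analyses for the Phase 1 part of the study". Section 2.2.2 defers duration of response, metastasis-free survival, time to metastases and time to ADT to Phase 2, but keeps durable response. Section 2.2.2.1 introduces it with "The following are the relevant endpoints corresponding to the secondary objectives in the phase 1 part of this study".

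SAP 6.6.2.2 then opens with a condition: "If more than three participants have a confirmed PSA response at month 6 then the number, proportion and 90% CIs" of durable response are given by treatment group in the EES, with a second summary in a responder subset. It gives no alternative presentation when the condition fails.

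SAP Section 7, which records changes to the planned analysis, has one entry: "The change from baseline for electrocardiograms have been added as a primary endpoint for the primary objective". The reporting condition is not mentioned.

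**The concern.** The condition is an outcome, and one closely tied to the endpoint: no one can be a durable responder without first being a confirmed responder. Whether the protocol's secondary analysis appears therefore depends on how well the treatment did. If it appears, the responder count was at least four. If that count was zero to three, the report has no durable-response count, proportion or interval, although the protocol calls for them.

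Sparse data do not force this. The main denominator is the EES, not the responders, so the proportion is defined at any count, including zero. A Jeffreys interval, the method SAP 6.6.2.1 names for PSA response, also exists at any count.

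The rule is also not fully specified. It does not say whether the threshold is counted across Phase 1 or within each treatment group, or whether a response at Month 6 means one still present at that visit or one reached by then.

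**Working it through.** **Inputs.**
- Threshold: more than three, so at least four (SAP 6.6.2.2).
- Phase 1 size: Protocol Table 5 gives 3–6, 6 and 6 participants completing dosing, so 3 + 6 + 6 = 15 to 6 + 6 + 6 = 18. For enrolment, SAP 2.3 says: "Approximately 25 participants will be enrolled into the Phase 1 of the study". The size of the EES is not known in advance.
- True response rate: 10% and 20% are borrowed from the Phase 2 sizing in Protocol 11.4; 30% is added to show a range. A common rate across the three cohorts is assumed.
- Any confirmed response is counted toward the threshold.

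**Reproducing the plan's figure.** Protocol 11.4 gives a 76.6% chance of four or more responders among 25 at a true rate of 20%, which is numerically the same threshold. With X binomial(n, p), P(X ≤ 3) = Σ C(n,k) p^k (1−p)^(n−k) for k = 0 to 3. For n = 25 and p = 0.2:

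0.0038 + 0.0236 + 0.0708 + 0.1358 = 0.2340, and 1 − 0.2340 = 0.7660. The stated 76.6% reproduces.

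**Chance that the summary is withheld, P(X ≤ 3).**

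| Assumed true rate | n = 15 | n = 18 | n = 25 | Counted within a cohort of 6 |
|---|---|---|---|---|
| 10% | 94% | 90% | 76% | 99.9% |
| 20% | 65% | 50% | 23% | 98% |
| 30% | 30% | 16% | 3% | 93% |

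If the trigger requires the response to be present at the Month 6 visit itself, the qualifying count can only be equal or smaller, so the summary would be withheld at least as often. The two readings do differ: the example participant in SAP Table 8 is at −49.38% at Month 6, yet is classed as a responder with a response at Month 8.

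**Direction of selection.** Given X ≥ 4 and a true rate of 20%, the mean observed PSA response rate is 31.4%, 27.7% and 23.1% for n = 15, 18 and 25. These are rates of PSA response, not of durable response. If each responder has the same chance q of being durable, whatever the number of responders, the expected durable rate given that it is shown is q times these values, against q × 20% unconditionally. The ratios are 31.4/20 = 1.57, 27.7/20 = 1.39 and 23.1/20 = 1.16. The constant q is an assumption; the upward direction follows from the durable count being part of the count that triggers the table.

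**Are the withheld results estimable?** The 90% Jeffreys limits are the 5th and 95th percentiles of Beta(x + 0.5, n − x + 0.5), with the lower limit set to 0 when x = 0.

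| Result | 90% interval |
|---|---|
| 0/18 | 0 to 10.0% |
| 3/18 | 6.3% to 34.4% |
| 0/25 | 0 to 7.3% |
| 3/25 | 4.5% to 25.7% |
| 0/6 | 0 to 26.4% |
| 3/6 | 20.9% to 79.1% |

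All can be calculated. The pooled intervals at zero are informative against the protocol's 10% and 20% reference rates. Those for a single cohort of 6 are wide.

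**The case against.** The strongest reply is that little is lost. SAP 6.6.2.1 reports confirmed PSA response with a 90% interval, by timepoint and overall, for each treatment group and without condition. It adds maximum percentage change, a waterfall plot, and a plot of every participant's PSA over time. Since the responder count caps the durable count, a poor result remains visible. Nothing confirmatory rests on the durable rate: Protocol 11.1 tests no formal hypothesis, and the decision to open Stage 2 uses PSA response. The rule is also written down before the analysis. And with about six per group, the intervals are too wide to say much.

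Most of this stands, and it limits the point. A reader might infer that poor efficacy would be concealed; the unconditional outputs show otherwise. A reader might infer that the trial's durable-response endpoint as a whole is at risk; this SAP governs Phase 1 only. A reader might also infer that the threshold was chosen with responder counts in hand. The trial is open-label, and the SAP is dated 31 October 2024, after protocol Version 5.0 (18 April 2024), which describes 14 treated participants. But the documents do not say whether counts were known, so that inference is unsupported.

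What the reply does not answer is the mismatch. The unconditional outputs do not supply the durable count, proportion and interval with the Month 8 missing-data rule of SAP 5.2.1. The individual curves are on a percentage scale, so the 0.2 ng/mL part of the progression definition cannot be read from them directly.

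**Conclusion.** The point holds as an undeclared, outcome-dependent narrowing of one descriptive Phase 1 summary that the protocol requires without condition. It does not amount to hiding a poor result.

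On the pooled reading, the summary is more likely than not to be withheld at a 10% true rate for every size considered. At 20% the chance runs from 23% to 65%. On the per-cohort reading it would almost never appear. These are illustrations, not predictions: they rest on response rates borrowed from Phase 2 sizing, one rate for all cohorts including the low-dose one, any confirmed response counting, and assumed denominators. The finding itself needs none of them, since it follows from the two sections read together and from the interval being calculable at zero to three responders.

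**What to change.** In SAP 6.6.2.2, delete the opening condition. Always present the count, proportion and 90% Jeffreys interval for durable PSA response among all EES participants, by treatment group and overall, and name the interval method in that section. If three or fewer participants respond, list them individually and omit only the interval in the responder subset. This also removes the ambiguities over how the threshold is counted and what a response at Month 6 means for it.

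Recording and justifying the condition in SAP Section 7 would cure the undeclared departure from the protocol, but would leave reporting dependent on the result. Deletion is preferable. The cost is one short table; no sample size, data collection or other analysis changes.
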